Research on motor recovery in patients with TBI is scarce compared with other neurologic diseases involving the brain, such as stroke [2]. Specifically, arm and hand paresis occurs in approximately 17% of TBI patients [5] and may limit an individual's ability to undertake activities of daily living (ADL). The recovery time of upper extremity weakness is different according to the mechanism of injury (patients with diffuse brain injury recover more slowly than those with focal injury), severity of initial weakness, and time spent unconscious [2]. Compared to stroke, motor recovery in patients with TBI is characterized by a low incidence, decreased severity, and good prognosis [2]. However, inspite of the difference in trajectory of recovery in early stages after stroke and TBI, there are similarities in the course of disease in chronic stages. In both conditions, motor defcitis are caused by injury to the corticospinal tracts or motor control centers in the brain. Furthermore, there is significant overlap in therapeutic approches for motor restoration [43]. Therefore, therapies tested in stroke population can be successfully applied in treatment for patients with TBI.

Multi-disciplinary rehabilitation has been shown to improve the experience of living with a long term neurological condition. Although we now understand that brain plasticity plays a

significant role and offers a window of opportunity to promote recovery, we still do not know how to maximize recovery [6]. Activity-based interventions hope to maximize neural plasticity [3], however, optimal doses and schedules of training have not been adequately established. Repetition is one parameter important for experience-dependent neural plasticity. Studies assessing US rehabilitation found that stroke and TBI survivors receive an average of 32–50 repetitions of upper extremity active and passive movement per therapy session, less than the 400-600 repetitions used in animal studies [3]. Although TBI survivors benefit from traditional therapy, it is clear that more is needed to attain full recovery, especially with severely affected individuals. Hence, various technologies to supplement therapy are being investigated, including robotic therapy.

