#### 10. Describe the means of analyzing the data and evaluating the results.

- State the anticipated methods to be used for analysis and interpretation of the data.
- The methods must compliment the design of the study and the nature of the data which is being collected.

As a primary analysis of therapeutic benefit, we will use a paired t-test to compare the difference between baseline and final evaluation at the end of the home use period. A similar comparison using the Box and Block Test results will be used as the primary analysis of functional benefit. For these primary analyses, critical alpha will be adjusted using the Bonferroni correction to account for Type 1 error.

Secondary analyses will assess changes over time in each outcome measure as well as correlations between satisfaction and measures of motor impairment and function (both perceived and actual). We anticipate that the therapeutic measures will increase initially before plateauing while functional measures are expected to increase slowly at first with

continued gains across the home use period. We expect that satisfaction will be positively correlated with perceived improvements in function.

We will use single subject analysis to evaluate changes over time for each outcome measure. In order to capture individual effects, baseline to end of home use outcomes data will be plotted, with outcome measure score on the vertical axis and time/transition through conditions (therapy/training to home use) on the horizontal axis. Visual inspection in the form of change in trend (i.e., a systematic variation in the slope of the data points from one phase to the next) will be used. [name] has some experience with single subject analyses as detailed in a paper accepted for publication that evaluated ankle foot orthoses effect on community ambulation outcomes in children with cerebral palsy.

Spearman's correlation will be used to assess the relationship between OPUS satisfaction with device and Fugl-Meyer Assessment of Motor Recovery upper limb subsection score, as well as OPUS satisfaction with device and OPUS functional status.

As a primary analysis of MRI-based measures, we will use a paired comparison between baseline and post training evaluation (prior to home use period). For the TMS-based measures, we will compare data between baseline, at week 9, after the end of the therapy and after the end of the home-use phase. We will evaluate changes over time for each outcome measure.

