## 11. Provide a BRIEF DESCRIPTION of how the estimated number of study subjects needed for this research was determined

- If this is a quantitative study provide the method of determining sample size estimates.
- If multiple studies are planned provide a power analysis or justification for each one.

To determine our sample size, we utilized data obtained from a previous pilot study [26]. In that study of 9 patients with stroke, a change in the Fugl-Meyer Assessment of Motor Recovery upper limb subsection score of  $3.2 \pm 2.91$  was reported to be statistically significant [26]. This data was used to calculate effect size (d = 1.107) because we do not have pilot data for TBI. Using the G\*Power computer program [53] this effect size was used to estimate sample size. For a 1-tailed matched pairs t-test (comparing baseline to final evaluation at end of home use period) we would need a total sample size of 11 to detect an effect size of 1.107 with a critical alpha of 0.05 and power of 0.95. In order to account for possible attrition in subject numbers we will recruit 20 persons with TBI or stroke. Furthermore, we estimated that we would need to screen 70 subjects to recruit 20.

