Study Part 3 –Therapy/Training: In addition to standard-of-care motor learning based therapy [33], we will follow the PERL ("Push Eat Reach Lift") Program recommended by Myomo, which consists of a 9 week, 18 session training plan. However, consistent with recommendations that best practices for the use of robotic devices be flexible, allowing therapists to tailor the therapy protocol and use of devices to an individual's level of motor impairment and rehabilitation goals [14], clinical judgment and subject progress will be used to either increase or decrease the number of therapy sessions and to determine the type of activities that are performed during training and therapy. Similar to Kim et al. [26], the sessions will be 1 hour typically 2 times a week but combine both therapy and training. Each week, there will be one session as needed that will combine therapy/training and orthotic assessment to ensure continued optimal fit and function of the device. Every second week, there will be one session that will combine therapy/training and outcomes evaluation.

The basic steps of the training program include:

- 1. Start in BICEP mode and HAND CLOSE mode. While seated, teach users to flex and extend the elbow while ignoring the hand, then switch and have them open and close the hand and ignore the elbow. Progress to sequential movements, e.g. close hand, bend elbow, open hand, relax elbow. Progress to simultaneous movements, e.g. flex elbow with closed hand; flex elbow with open hand; extend elbow with open hand; extend elbow with closed hand. This can all be repeated with the subject standing. This should be done two times a day for 10-15 minute sessions. Once these are mastered the subject can move to step 2.
- 2. Have the subject engage in task specific practice in BICEP and HAND OPEN modes. Tasks may include stacking cups or other items, grasping and moving items (e.g. cotton balls, items from purse or bag), hand to mouth tasks (e.g. bring napkin up to mouth, drink from cup or bottle), and finger extenders may be used to grasp paper, playing cards, take paper money out of a wallet. These activities should be attempted two times a day for five minutes each and progress to one time a day for 10 minutes each category. Once these are mastered the subject can move to step 3.

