#### INCLUSION CRITERIA.

- Over 18 years of age
- Minimum 6 months since injury or stroke
- Full passive range of motion at the elbow, forearm, wrist, and hand [26]
- Active shoulder flexion of at least 30 degrees and active shoulder abduction of at least 20 degrees
- Minimum of 1/5 on manual muscle test of elbow flexion and extension (biceps and triceps) [26] and forearm flexors and extensors
- Ability to generate volitional, consistent, and detectable EMG signals from the upper arm and forearm sensor sites with wrist in neutral or flexed positions as detected by the MyoPro Motion-G software
- MAS score  $\leq 3$  for the biceps, triceps, supinators and pronators of the impaired arm
- Able to read and comprehend the English language
- Demonstrate ability to follow two-stage command
- Cognitive abilities sufficient to perform testing and training protocols
- Able to tolerate functional tasks for 60 minutes without excessive fatigue [26]
- Medically and psychologically stable [26]
- At home support from a family member or care giver if needed [26]

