Although the study will require 22 weeks of participation, subjects are considered to have a static neurological injury and hence we should not need to obtain ongoing consent or re-assess the capacity to consent over the course of the study.

49. Will there be an opportunity for potential subject to take the consent form home to discuss participation and options with family members?

- 50. List by role who will be obtaining informed consent from subjects or their legally authorized representatives:
  - ex. study coordinator, co-investigator, research nurse, research assistant, PI Study PI or Physical Therapist
- 51. Please describe how informed consent will be obtained from subjects who do not read or understand English;
  - identify any languages likely to be encountered, and attach a copy of a translated and authenticated informed consent document
  - It is appropriate to indicate that you do not anticipate encountering potential subjects who do not speak English based on the population to be studied

We will not be able to include subjects who do not understand English.

- 52. Describe who (by Role ex. PI, Coordinator, etc.) and how it will be determined that subjects and/or legally authorized representative understand the research and their rights.
  - ex. question and answer, repeat back parts of the research, describe a procedure...etc

This will be determined during the consenting process and during the examination completed by the neurologist, reviewed by the necessary study personnel (PI, therapist). Candidates will be encouraged to ask questions and repeat back key part of the research. Subjects will be encouraged to ask questions.

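### Both primary tests run from a single week-1 score, and the week-5 test that could show change before therapy is neither fixed ahead of therapy nor analysed on its own

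*Combined protocol and SAP*

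**What the plan says.** Item 10 gives the therapeutic primary analysis as "we will use a paired t-test to compare the difference between baseline and final evaluation at the end of the home use period". For function, "A similar comparison using the Box and Block Test results will be used as the primary analysis of functional benefit", and across the two "critical alpha will be adjusted using the Bonferroni correction to account for Type 1 error". Item 10 does not name the therapeutic measure. Item 11 sizes the study on the Fugl-Meyer upper limb score, with a "total sample size of 11 to detect an effect size of 1.107 with a critical alpha of 0.05 and power of 0.95", and recruits 20. Item 14 records no placebo group, no other control group and no randomization.

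In Table 2 the Fugl-Meyer, BBT and CAHAI are each tested once before the orthosis is delivered, at week 1, without the orthosis. Each is tested next at week 5, with and without it. Between these, Item 13 describes casting, about two weeks of fabrication, fitting with calibration, and delivery. Therapy first appears in Part 3, which starts at week 5. Of Part 3 it says: "Every second week, there will be one session that will combine therapy/training and outcomes evaluation". The order within that session is not stated.

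Item 10 also plans secondary analyses of change over time and single-subject plots. The only phases it names for the plots are therapy/training and home use.

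**The concern.** With no comparison group, the paired test attributes the whole mean change since week 1 to the intervention. A subject who scores better at the second test because the tasks are now familiar contributes to the reported benefit just as a responder does.

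The schedule already contains a partial safeguard: a second no-orthosis measurement after about four weeks without described study therapy. The safeguard is lost if the week-5 evaluation follows some of the first therapy session or a run with the orthosis. Even a clean week-5 score would go unreported as a pre-therapy change, because no analysis is assigned to it. The single-subject plots have the same gap. They look for a change of slope between phases, and one baseline point has no slope.

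At stake is how far the primary results can be read as effects of orthosis use, which is how the Specific Aims in Item 9 are worded.

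**Working it through.** **Inputs from the documents.** Planned Fugl-Meyer change 3.2, SD of change 2.91, d = 1.107, one-tailed alpha 0.05, power 0.95, 20 recruited (Item 11); Bonferroni over two primary analyses (Item 10); tests at weeks 1, 5 and 22 (Table 2).

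**Assumed.** The pilot SD of 2.91 also applies to the week 1 to 5 and week 5 to 22 changes. Testing is one-sided at 0.05/2 = 0.025. All 20 subjects are analysed. Step and drift sizes are shown as ranges because the documents give none.

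**1. The plan's own figure.** Exact paired-t power with d = 1.107 and one-sided 0.05 gives N = 11 (power 0.961). Using 3.2/2.91 = 1.0997 also gives N = 11 (0.959). At one-sided 0.025, N is 13, which 20 recruits cover. The arithmetic is sound, but it presumes zero expected change without the orthosis.

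**2. Share of the planned effect from a one-time step.** 0.5/3.2 = 16%; 2/3.2 = 63%.

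**3. Chance of a significant week 1 to 22 result with no intervention effect.** Power of the paired t-test with noncentrality sqrt(20) × b/2.91, 19 df, one-sided 0.025:

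| Non-intervention change b (assumed, points) | Probability of significance |
|---|---|
| 0 | 0.025 |
| 0.5 | 0.11 |
| 1.0 | 0.31 |
| 1.5 | 0.59 |
| 2.0 | 0.83 |

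**4. What a week-5 reference removes.** A step complete by week 5 is removed in full. Steady linear drift is not: 17 of the 21 weeks remain, or 17/21 = 81%. If drift alone produced 3.2 points over 21 weeks, 3.2 × 17/21 = 2.59 points would still be counted.

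**5. Precision of the week 1 to 5 change.** 95% CI half-width = t(19, 0.975) × 2.91/sqrt(20) = 2.093 × 0.651 = 1.36 points. The drift in step 4 amounts to 3.2 × 4/21 = 0.61 points over four weeks, well inside that width.

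**6. Power of the week-5 comparison.** n = 20, one-sided 0.025, SD 2.91:

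| Part of the 3.2 points arising before week 5 | Power |
|---|---|
| 0 | 0.997 |
| 0.5 | 0.976 |
| 1.0 | 0.894 |
| 1.5 | 0.698 |

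**7. Why not subtract each subject's pre-therapy slope.** Suppose all change variance is independent occasion error, so the variance per occasion is 2.91²/2. Extrapolating the four-week slope over 17 weeks gives SD = sqrt[(1 + 5.25² + 4.25²) × 2.91²/2] = 14.1 and power 0.16 at n = 20. That analysis is not feasible.

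None of this can be computed for the BBT, for which the documents give no variance.

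**The case against.** Several points on the other side stand.

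- **Week 5 is not ignored.** It enters the secondary analyses of change over time and the plots. What is missing is a named week 1 to 5 contrast and a fixed test order.
- **Aim 2 has another safeguard.** From week 5 the BBT and CAHAI are done with and without the orthosis at the same visit, and slow recovery between visits cannot create that contrast. It does not protect the week 1 to 22 comparison named as primary.
- **The interval is not proven untreated.** Fitting and calibration fall inside it, and nothing says usual care is withheld or where the device stays after delivery. Pre-therapy is the accurate label.
- **The study is described as observational.** Item 10 nevertheless calls the results therapeutic and functional benefit.

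Two stronger readings are tempting. A reader might infer that regression to the mean inflates the result. The documents give this little support: entry is not selected on Fugl-Meyer or BBT, and the motor criteria are mainly floors, which do not favour apparent improvement.

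A reader might also infer that the plan contradicts itself on residual recovery, setting "patients with diffuse brain injury recover more slowly than those with focal injury" and "Minimum 6 months since injury or stroke" against "subjects are considered to have a static neurological injury". The first describes recovery time in general and does not say that recovery continues past six months. The last explains why consent is not repeated. Late recovery is limited by the entry rule, not excluded, and the documents do not show that it occurs.

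**Conclusion.** The point holds as a cheap improvement to a single-arm design. Any practice step or other change before therapy is counted as benefit in both primary analyses. The one scheduled measurement that could expose it is not protected from contamination and has no analysis of its own.

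The size is conditional. A step of 0.5 to 2 points would be 16% to 63% of the planned Fugl-Meyer effect, but that range is assumed and the SD of 2.91 comes from change under treatment. The documents do not establish that the week 1 to 22 estimate is biased upward, only that the plan could not tell if it were.

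The remedy is also limited. It deals with a step and leaves 81% of any linear drift. The motor-learning therapy given alongside the device stays confounded with it. With a half-width of about 1.4 points, the week 1 to 5 change is too imprecise to serve as a pass/fail rule for claiming benefit, so it should be reported and not used as a gate.

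**What to change.** **Item 13 and Table 2.** State that the week-5 no-orthosis Fugl-Meyer, BBT and CAHAI are completed before the first therapy/training session and before any with-orthosis run.

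**Item 10.**

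- Keep the week-1-referenced primary tests.
- Report the week 1 to 5 change in each measure with its 95% CI, labelled as pre-therapy change.
- Add a sensitivity analysis that repeats both primary paired comparisons with week 5 as reference, using no-orthosis scores. Item 10 does not say which BBT condition is primary, so state this.
- Show weeks 1 and 5 as the pre-treatment phase in the single-subject plots.
- State the limits: the sensitivity analysis removes a step effect only; slow drift and the concurrent therapy remain confounded with the orthosis.

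**Cost.** A few sentences, with no new visit, test or staff. The week-5 tests must open the first therapy week, and the week-5-referenced gain may be smaller than the primary one.

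### Single-step Bonferroni on the two primary tests is valid, but Holm's step-down procedure keeps the same family-wise error and gives more power for each claim and for both together

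*Combined protocol and SAP*

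**What the plan says.** Item 10 (analysis) sets two primary analyses. For the first: "As a primary analysis of therapeutic benefit, we will use a paired t-test to compare the difference between baseline and final evaluation". For the second: "A similar comparison using the Box and Block Test results will be used as the primary analysis of functional benefit". They correspond to the two Specific Aims in Item 9, so each test supports its own claim. On multiplicity, Item 10 says: "For these primary analyses, critical alpha will be adjusted using the Bonferroni correction to account for Type 1 error".

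Item 10 does not state the number of tests, the adjusted threshold or the sidedness, and it mentions no stepwise or ordered procedure. No simultaneous confidence intervals are planned anywhere.

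Item 11 (sample size) rests on the Fugl-Meyer score alone. It describes the test as "For a 1-tailed matched pairs t-test" and uses an effect size of 1.107, a "critical alpha of 0.05 and power of 0.95", which gives 11 subjects. Twenty are to be recruited to allow for attrition. No effect size, standard deviation or power is given for the Box and Block Test.

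**The concern.** With two tests, Bonferroni holds each at alpha/2 whatever happens to the other. Once one claim has been established at alpha/2, its share of alpha can pass to the other claim without raising the family-wise error above alpha. Holm does this and single-step Bonferroni does not. The usual reason for keeping the single-step form is that simultaneous confidence intervals follow from it simply, and this plan has none.

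What is at stake is a primary claim lost with a one-tailed p-value between 0.025 and 0.05 although the other primary has succeeded. In a study of 11 to 20 people, where one of the two primaries has no power calculation, that is a realistic outcome.

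**Working it through.** **Inputs.** Effect size 1.107, one-tailed testing, alpha 0.05, N = 11 and 20 recruited are from Item 11. The Bonferroni rule is from Item 10. Three things are assumed: a family of two tests; a correlation of 0.5 between the two changes; and the Box and Block effect, which is varied. Fugl-Meyer is taken as the therapeutic primary because Item 11 is sized on it.

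**The plan's own figure.** Power of a one-tailed paired t-test is 1 − F(t(1−α, n−1)), where F is the noncentral t distribution function with n − 1 degrees of freedom and noncentrality d√n. For n = 11 and d = 1.107, the noncentrality is 1.107 × 3.317 = 3.67.
- At alpha 0.05, power is 0.961 with n = 11 and 0.943 with n = 10, so N = 11 reproduces.
- The pilot figures give 3.2/2.91 = 1.0997 instead of 1.107. N is still 11 (power 0.959).
- At the Bonferroni level of 0.025, power with n = 11 is 0.910.

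**Error control of Holm** (smaller p against 0.025; if significant, larger p against 0.05).
- Both nulls true: a false claim needs at least one p ≤ 0.025, with probability at most 0.025 + 0.025 = 0.05.
- One null true: a false claim needs that p ≤ 0.05, with probability at most 0.05.

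Simulation agrees. With n = 11 and both nulls true, the family-wise error is 0.046 under either method. With only the Box and Block null true and Fugl-Meyer d = 1.107, Holm's error is 0.049 with n = 11 and 0.050 with n = 20.

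**Power** (200,000 replicates of bivariate normal changes, one-tailed, correlation 0.5).

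Fugl-Meyer effect fixed at 1.107:

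| n | Box and Block d | Box and Block power, Bonferroni → Holm | Fugl-Meyer power, Bonferroni → Holm |
|---|---|---|---|
| 11 | 0.3 | 0.145 → 0.234 | 0.911 → 0.912 |
| 11 | 0.6 | 0.44 → 0.57 | 0.91 → 0.92 |
| 11 | 0.8 | 0.668 → 0.782 | 0.910 → 0.930 |
| 11 | 1.107 | 0.91 → 0.95 | 0.91 → 0.95 |
| 11 | 1.4 | 0.986 → 0.992 | 0.911 → 0.959 |
| 16 | 0.6 | 0.61 → 0.74 | 0.985 → 0.986 |
| 20 | 0.6 | 0.72 → 0.83 | 0.997 → 0.997 |
| 20 | 1.107 | 0.997 → 0.999 | 0.997 → 0.999 |

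With n = 11 and both effects at 1.107, power to establish both claims rises from 0.85 to 0.925. Power to establish at least one is 0.975 under both methods. The two methods agree on this last measure in every scenario, because the first Holm step is the Bonferroni test.

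**Sensitivity to the Fugl-Meyer effect.** Holm helps Box and Block only after Fugl-Meyer has passed 0.025. With n = 11 and Box and Block d = 0.6, the Box and Block gain is about 0.14 if the Fugl-Meyer effect is 1.107, 0.10 if it is 0.8, 0.06 if it is 0.6 and 0.03 if it is 0.4.

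**Sensitivity to sidedness.** Item 10 gives none. With two-sided tests, n = 11 and both effects at 1.107, power per claim rises from 0.83 to about 0.89, and power for both from 0.72 to 0.835.

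**The case against.** Bonferroni is pre-specified and valid. The documents show no contradiction, bias or inflated error on this point. That stands, so the point is a suggestion about efficiency and not a fault.

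Two stronger readings are tempting, and neither is supported.
- A reader might infer that Holm is more powerful in every sense. It is not: the chance of showing at least one benefit is the same.
- A reader might also infer that the functional claim gains most, since it has no planning effect size. A missing effect size does not make the effect small. The larger gain falls on whichever outcome has the smaller effect, and the documents do not say which that is. At a Box and Block effect of 1.4, Fugl-Meyer gains about 0.05 and Box and Block 0.006. Item 10 itself expects functional measures to keep improving through home use while therapeutic measures level off.

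The gains also depend on the assumptions. The effect of 1.107 comes from nine stroke patients, and ending with 11 completers means losing 9 of 20 (45%), with no dropout rate stated. If all 20 complete and both effects are near 1.107, almost nothing is gained.

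Ordinary two-sided 95% intervals would sit badly beside one-tailed Holm tests. Every extra claim has a one-tailed p between 0.025 and 0.05, and for such a p the two-sided 95% interval includes zero. That stands, and the fix allows for it.

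Finally, Item 10 does not name the therapeutic measure, and Item 13 has the Box and Block Test done with and without the orthosis without saying which is primary. These gaps affect the existing Bonferroni sentence equally, so they are no reason to keep it.

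**Conclusion.** The point holds as a free improvement. Holm dominates the planned correction: it has the same family-wise error control, more power for each claim and for both, and the same power for at least one. This ordering needs no assumption about effects or correlation.

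The size does need assumptions. Over the scenarios examined, the gain for a single claim runs from almost nothing to about 0.14. It is about 0.04 per claim with 11 completers and both effects at 1.107, and about 0.002 with 20. The figures assume two tests, one-tailed testing as in Item 11 and a correlation of 0.5. The Box and Block effects are illustrative because the documents give none.

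**What to change.** Replace the Bonferroni sentence in Item 10 with: *The two primary p-values, with the same sidedness as the sample-size calculation (one-tailed, Item 11), will be tested by the Holm step-down procedure at family-wise alpha 0.05: the smaller against 0.025 and, if significant, the larger against 0.05.*

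Report confidence intervals whose sidedness and level match the tests, for example one-sided 95% bounds or two-sided 90% intervals, labelled as unadjusted. The label matters because such an interval can exclude zero when Holm does not reject, as when both p-values lie between 0.025 and 0.05. Do not present two-sided 95% intervals as the companion to a one-tailed 0.05 test.

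The cost is this wording, with no extra patients, visits or data. It must be settled before results are seen. The one drawback is that simultaneous intervals matching Holm are less simple to construct, and the plan specifies none.
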